## 4. OBJECTIVES AND ENDPOINTS

Objectives	Endpoints
Primary	

 
To evaluate the safety of long-term treatment with FF/UMEV/VI combination therapy
 
	
 
Incidence and type of adverse events (AE)/serious adverse events (SAE)
 

Secondary	

 
To evaluate the safety of FF/UMEV/VI combination therapy
 
	
Secondary Endpoints
 
 
Blood pressure/pulse measurements
 
12-lead electrocardiogram (ECG)
 
Clinical laboratory tests (hematology, biochemistry and urinalysis)
 

Other	

 
To evaluate the efficacy of FF/UMEV/VI combination therapy
 
	
Other Endpoints
 
 
Mean change from baseline in trough Forced Expiratory Volume in 1 second (FEV1) at Week 24 and Week 52
 
Mean change from baseline in Asthma Control Questionnaire-7 (ACQ-7) total score at Week 24 and Week 52
 
Mean change from baseline in St. George's Respiratory Questionnaire (SGRQ) total score at Week 24 and Week 52
 
Mean change from baseline in the Asthma Quality of Life Questionnaire (AQLQ) total score at Week 24 and Week 52
 
Unscheduled asthma-related healthcare resource utilization over the 52 weeks of the treatment period
 
Annualized rate of severe asthma exacerbations
 
Annualized rate of moderate/severe asthma exacerbations
 

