**Table 7      The Special interest groups and subgroups**

Special interest AE group	Special interest AE subgroup
Cardiovascular effects	Cardiac arrhythmia
	Cardiac failure
	Cardiac ischemia
	Stroke
Anticholinergic syndrome	-
Urinary retention	-
Dry mouth / drying of airway secretions	-
Gastrointestinal obstruction	-
Antimuscarinic ocular effects / Corticosteroids associated eye disorders	Glaucoma (antimuscarinic/corticosteroid)
	Cataracts (corticosteroid)
Pneumonia and LRTI	Pneumonia
	LRTI excluding pneumonia
Adrenal suppression	-
Decreased bone mineral density and associated fractures	-
Effects on glucose	-
Effects on potassium	-
Tremor	-
Asthma intubations, and deaths	-
Hypersensitivity	-
Local steroid effects	-

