**Table 8      Protocol Required Safety Laboratory Assessments**

Laboratory Assessments	Parameters			
Hematology	Platelet count	RBC Indices:		WBC count with differential:
	Red blood cell (RBC) count	MCV		Neutrophils
	Hemoglobin	MCH		Lymphocytes
	Hematocrit			Monocytes
				Eosinophils
				Basophils
Clinical Chemistry 	Blood urea nitrogen (BUN)	Potassium	AST (SGOT)	Total and direct bilirubin
	Creatinine	Sodium	ALT (SGPT)	Total protein
	Glucose	Calcium	Alkaline phosphatase	Albumin
Routine Urinalysis	
 
pH, glucose, protein, blood and ketones by dipstick
 
Specific gravity, Microscopic examination (if blood or protein is abnormal)
 
			
Other Screening Tests	
 
Follicle-stimulating hormone and estradiol (as needed in females of non-reproductive potential only)
 
Serum/urine hCG pregnancy test (see the SoA in Table 1)
 
			

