#### 10.3.2. Safety Analyses

All safety analyses will be performed on the ITT Population.

Endpoint	Statistical Analysis Methods
Primary	
The primary endpoint is incidence and type of AEs/SAEs. This endpoint will be summarized using the following two approaches:
 
 
1. Summary statistics will be provided for the integration of the groups and for each group separately (only FF/UMEC/VI 100/62.5/25 mcg, only FF/UMEC/VI 200/62.5/25 mcg and switching medication from FF/UMEC/VI 100/62.5/25 mcg to FF/UMEC/VI 200/62.5/25 mcg).
 
2. Summary statistics will be provided by the dose received at the time of experiencing the AE. (FF/UMEC/VI 100/62.5/25 mcg and FF/UMEC/VI 200/62.5/25 mcg)
 
 
The number and proportion of subjects experiencing at least one AE will be calculated and presented by system organ class (SOC) and by preferred term (PT). Summary statistics will also be presented for all AEs, treatment-related AEs, SAEs, AEs leading to treatment or study discontinuation, and AESI.

Secondary	
Secondary endpoints will be summarized using the approach described in approach 1 above (i.e., provided for only FF/UMEC/VI 100/62.5/25 mcg, only FF/UMEC/VI 200/62.5/25 mcg and switching medication from FF/UMEC/VI 100/62.5/25 mcg to FF/UMEC/VI 200/62.5/25 mcg).
 
Specific details will be provided in the Reporting and Analysis Plan (RAP).

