8.5. Clinical Laboratory Analyses

Laboratory evaluations including the analyses of Chemistry laboratory tests, Hematology laboratory tests, Urinalysis, and liver function tests will be based on GSK Core Data Standards. The details of the planned displays are in [Appendix 11: List of Data Displays](#).

Clinical laboratory will be measured at visit 1 (screening visit), 4 (Week 12), 5 (Week 24), 7 (Week 52) or EW. and will be summarized by dose group.

Raw value and change from baseline for laboratory data will be summarized by dose group and total for each visit.

Shifts from baseline relative to the normal range will be also summarized by dose group and total for each visit.

The number of participants with worst case chemistry or hematology will be summarized by test and category. The categories for normal range are: To Low, To Normal or No Change, To High. The categorization is determined by comparing the baseline category to the worst case post-baseline category. The determination of the worst case post-baseline takes into account both planned and unscheduled assessments. The percentages are based on the number of participants in the dose group with data for the test post-baseline. Participants with missing baseline value are to be assumed to have normal/within range baseline value. Note that if a subject has both a decrease ‘To Low’ and an increase ‘To High’, then the subject is counted in both the ‘To Low’ and ‘To High’ categories, so the percentages may not add to 100%.

The number of participants with worst case protein (category: NEG, TRA, 1+, 2+, 3+) or occult blood (category: NEG, TRA, 1+, 2+, 3+) urinalysis results will be summarized by test and category. The categories for worst case are: No Change/Decresed, Any Increase, Increase to TRA, Increase to 1+, Increase to 2+, Increase to 3+. The categorization is determined by comparing the baseline category to the worst case post-baseline category. The determination of the worst case post-baseline takes into account both planned and unscheduled assessments. The percentages are based on the number of participants in the dose group with data for the test post-baseline. Participants with missing baseline value are to be assumed to have normal/within range baseline value.

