No.	Population	IDS / Example Shell	Title	Programming Notes	Deliverable [Priority]
62.	ITT	AE8	Listing of Non-Fatal Serious Adverse Events	ICH E3 Fatal and Non-Fatal SAEs are combined into a single listing for ClinPharm studies (i.e., "Listing of Serious Adverse Events").	SAC [1]
63.	ITT	AE14	Listing of Reasons for Considering as a Serious Adverse Event	ICH E3	SAC [1]
64.	ITT	AE8	Listing of Adverse Events Leading to Withdrawal from Study / Permanent Discontinuation of Study Treatment	ICH E3	SAC [1]
65.	ITT	AE8	Listing of Adverse Events of Special Interest	ICH E3 Required for studies where interventions other than withdrawal from treatment or study are possible.	SAC [1]
Hepatobiliary (Liver)					
66.	ITT	MH2	Listing of Medical Conditions for Participants with Liver Stopping Events	IDS	SAC [1]
67.	ITT	SU2	Listing of Substance Use for Participants with Liver Stopping Events	IDS	SAC [1]
68.	ITT	LIVER5	Listing of Liver Monitoring/Stopping Event Reporting	IDS	SAC [1]

CONFIDENTIAL

207236

ICH: Listings					
No.	Population	IDSL / Example Shell	Title	Programming Notes	Deliverable [Priority]
All Laboratory					
69.	ITT	LB5	Listing of Chemistry Values for Subjects with Any Value Outside Normal Range	ICH E3 May be split into separate listings by chemistry, hematology, etc. Display ALL labs for a subject who experienced a value of potential clinical importance.	SAC [1]
70.	ITT	LB5	Listing of Haematology Values for Subjects with Any Value Outside Normal Range	ICH E3 May be split into separate listings by chemistry, hematology, etc. Display ALL labs for a subject who experienced a value of potential clinical importance.	SAC [1]
71.	ITT	UR2A	Listing of Urinalysis Data (Protein and Occult Blood)	Protein and occult blood only. All subjects data need to be displayed.	SAC [1]
ECG					
72.	ITT	EG3 (modified)	Listing of ECG Values for Subjects with any Abnormal ECG Finding	IDSL Required for ClinPharm studies only.	SAC [1]
73.	ITT	EG5	Listing of Abnormal ECG Findings	IDSL Required for ClinPharm studies only.	SAC [1]

CONFIDENTIAL

207236

ICH: Listings					
No.	Population	IDSL / Example Shell	Title	Programming Notes	Deliverable [Priority]
Vital Signs					
74.	ITT	VS4	Listing of Vital Signs	IDSL Required for ClinPharm studies only.	SAC [1]

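### Urinalysis is part of a secondary safety endpoint, but the SAP reports only dipstick protein and occult blood; urine glucose and ketones, among other collected parameters, are in no specified laboratory output.

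*SAP*

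**What the plan says.** **Endpoint.** Protocol Section 4 includes among the secondary safety endpoints "Clinical laboratory tests (hematology, biochemistry and urinalysis"). SAP Section 2.2 repeats this.

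**Collection.** Protocol Table 8 (Section 9.4.4) requires "pH, glucose, protein, blood and ketones by dipstick", and also "Specific gravity, Microscopic examination (if blood or protein is abnormal"). The Schedule of Activities places urinalysis at Visits 1, 4, 5 and 7 and at early withdrawal.

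**Commitment.** Protocol Section 10.3.2 states: "Secondary endpoints will be summarized using the approach described in approach 1 above". It leaves the specifics to the reporting and analysis plan.

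**Planned reporting.** SAP Section 8.5 has a general sentence, "Raw value and change from baseline for laboratory data will be summarized by dose group and total for each visit", and one paragraph specific to urinalysis, which begins "The number of participants with worst case protein (category: NEG, TRA, 1+, 2+, 3+) or occult blood". For the displays it refers to Appendix 11. There, urinalysis has one interim table (2.25), one final table (12.44) and one final listing (71). The programming note to Listing 71 reads: "Protein and occult blood only. All subjects data need to be displayed".

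**Declared changes.** SAP Section 2.1 reports no departure from the protocol's planned analysis.

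**The concern.** The protocol collects a full dipstick as part of a named endpoint, and the SAP reports two of its analytes. The note to Listing 71 shows that this is a stated restriction and not missing detail, yet neither document gives a reason for it.

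An analyte with no laboratory display has one remaining route into the report: the investigator judges a change clinically relevant and records it as an adverse event (Protocol Section 9.4.4 and Appendix 3). In an open-label study without a comparator, systematic laboratory displays are a useful complement to that judgement. A drift in dipstick grades that no investigator thought worth recording would not be visible.

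Urine glucose and ketones deserve particular attention because "Effects on glucose" is one of the adverse event groups of special interest in Protocol Table 7. SAP Section 8.3 builds that group from reported adverse event terms, so a urine result not recorded as an event cannot enter it. The gap affects both the Week 24 package, which is intended for the Japanese submission, and the final report.

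**Working it through.** No hypothesis, power or sample-size figure is involved, and the plan gives no figure of its own to reproduce. The check compares what is collected with what is displayed.

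**Step 1: collected parameters (Protocol Table 8) against SAP Section 8.5 and Appendix 11**

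| Parameter | Worst-case summary (Tables 2.25, 12.44, as defined in Section 8.5) | Interim listing | Final Listing 71 |
|---|---|---|---|
| Protein | yes | none | yes |
| Blood | yes | none | yes |
| Glucose | no | none | no |
| Ketones | no | none | no |
| pH | no | none | no |
| Specific gravity | no | none | no |
| Microscopy (conditional) | no | none | no |

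Of the five dipstick analytes, two are covered and three are not. Specific gravity and microscopy are also uncovered.

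**Step 2: could another display catch them?** The tables of values, changes from baseline and shifts against the normal range exist only for chemistry (2.19 to 2.21; 12.38 to 12.40) and hematology (2.22 to 2.24; 12.41 to 12.43). The interim laboratory listings (26 and 27) are for chemistry and hematology, as are final Listings 69 and 70. The non-ICH listings contain no urinalysis. The general sentence in Section 8.5 on raw values and changes therefore has no matching urinalysis display.

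**Step 3: volume of undisplayed urine glucose and ketone results.** Inputs:
- planned enrolment of 110, with 100 expected to complete (Protocol Section 10.1);
- scheduled post-baseline urinalysis at Visits 4, 5 and 7, so 3 visits (Schedule of Activities);
- 2 analytes.

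Formula: visits x participants x analytes.
- Final, full retention: 3 x 110 x 2 = 660.
- Final, the 100 expected completers alone: 3 x 100 x 2 = 600, plus whatever participants who withdraw contribute before or at the early withdrawal visit.
- Interim (Visits 4 and 5), full retention: 2 x 110 x 2 = 440.

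These are counts of results. The documents give no expected rate of abnormal urine glucose or ketones, so the counts cannot be turned into a number of missed findings.

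**Step 4: what covers glucose by another route?** Serum glucose is in the chemistry panel of Protocol Table 8 and is drawn at the same visits as the urinalysis. It is tabulated at interim (2.19 to 2.21) and final (12.38 to 12.40), and participants with out-of-range chemistry are listed in both (Listings 26 and 69). Table 8 contains no blood ketone test, so urine ketones have no counterpart.

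**The case against.** The strongest reply is that glucose is already well reported. Serum glucose is quantitative, measured centrally on pre-dose samples, and displayed at both analyses; hyperglycaemia events are tabulated as events of special interest. This stands, and it is the main reason the point is modest.

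A reader might infer that serum glucose cannot stand in for the dipstick because it is a spot value without dietary control. The documents do not support that. The dipstick is also a spot test at the same visits, and the absence of dietary restrictions (Protocol Section 6.3.1) applies equally to both.

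A reader might also infer that the SAP dropped the part of urinalysis most relevant to the product. That goes too far. The risk assessment in Protocol Section 3.3.1 does not list glucose effects, the special-interest tables do not attribute the glucose group to a particular component, and nothing links urine ketones to any special-interest group. Table 8 offers a possible reason for the SAP's choice, since abnormal blood or protein triggers microscopy, although the SAP does not invoke it.

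Nor is this clearly a broken protocol commitment. Section 10.3.2 delegates detail to the analysis plan and does not promise every analyte. Urinalysis is summarized, in part. The silence of SAP Section 2.1 is an omission of disclosure, not proof of a deviation.

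Two wordings might be read as leaving the restriction open: the titles of Tables 2.25 and 12.44 name no analytes, with change categories to follow the laboratory dataset, and Section 8.5 cites the sponsor's core data standards. Neither is enough. Section 8.5 defines the table and names two tests, it refers to Appendix 11 for the displays, and the Listing 71 note is explicit.

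**Conclusion.** The gap in displays is real and follows directly from the text. As specified, urine glucose and ketones, and also pH, specific gravity and microscopy, are in no laboratory table or listing at either analysis, although urinalysis is a named part of the secondary safety endpoint. The restriction is neither explained nor disclosed.

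Its weight is modest. Serum glucose from the same visits is fully displayed, and a urine change judged clinically relevant would still appear among the adverse events. The loss is mainly urine ketones and corroborating urine glucose data: at most 660 scheduled post-baseline results by the final analysis (440 by Week 24), fewer to the extent that the planned drop-out of about 10% leaves visits missed. A reader might take 660 as a measure of missed safety signals; it is an upper bound on undisplayed results and says nothing about how many would be abnormal.

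The conclusion assumes that the tables will be programmed as Section 8.5 defines them and that the core data standards, which are not reproduced in the SAP, add no further urinalysis display. It does not bear on the primary endpoint.

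**What to change.** 1. In SAP Section 8.5, extend the worst-case urinalysis summary (Tables 2.25 and 12.44) to urine glucose and ketones, using the grades the laboratory reports and the existing rule for change from baseline.
2. Remove the protein-and-blood restriction from the title and note of Listing 71, so that all collected urinalysis parameters are listed.
3. Add the same listing to the interim set in Section 11.11.9.

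If the sponsor prefers to keep the restriction, the minimum is to state it with its reason in SAP Section 2.1. That discloses the gap without closing it.

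The cost is a short SAP edit, a few more table rows and listing columns, and one extra interim listing. No new samples, visits or procedures are needed.

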8.6. Other Safety Analyses

The analyses of non-laboratory safety test results including ECGs and vital signs will be based on GSK Core Data Standards, unless otherwise specified. The details of the planned displays are presented in [Appendix 11: List of Data Displays](#).

8.6.1. Vital signs

Vital signs will be measured at every clinical visit and will be summarized by dose group and total.

Raw value and change from baseline for Vital signs will be summarized by dose group and total for each visit.

8.6.2. ECG

12-lead ECGs are measured at Visit 1, 3, 5 and 7, and at Early Withdrawal visit. The ECG measurements of interest are QTc (F), heart rate, and PR interval. All ECG data present in the database will be considered valid and will be reported (even if the ECG had a technical error).

Raw value and change from baseline for ECG values will be summarized by dose group and total for each visit.

A ‘maximum post-baseline’ QTc (F), PR interval, and heart rate value will be derived as the maximum on-treatment value recorded at any scheduled, unscheduled, or EW visit after the start of study treatment.

QTc (F) values (including ‘maximum post-baseline’) will be categorized as follows: $\leq 450\text{msec}$, >450 to $\leq 480\text{msec}$, >480 to $\leq 500\text{msec}$, >500 to $\leq 530\text{msec}$ and $>530\text{msec}$. Change from baseline QTc (F) values (including change to ‘maximum post baseline’) will be categorized as follows: $\leq -60\text{msec}$, >-60 to $\leq -30\text{msec}$, >-30 to $\leq 0\text{msec}$, >0 to $\leq 30\text{msec}$, >30 to $\leq 60\text{msec}$, and $>60\text{msec}$.

An ‘any time post-baseline’ ECG interpretation will be derived as the worst on-treatment interpretation recorded at a scheduled, unscheduled, or EW visit after the start of study treatment. The worst case post-baseline is defined as:

- ‘Abnormal’ if any assessment during treatment period is evaluated as ‘Abnormal’
- ‘Unable to evaluate’ if all assessments during treatment period are ‘Unable to evaluate’
- ‘Normal’ if any assessment during treatment period is evaluated as ‘Normal’ and there are no assessments evaluated as ‘Abnormal’ during treatment period

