### 8.1.2. QTc Stopping Criteria

Details on performing ECG assessments can be found in Section [9.4.3..](#)

- The QTcF (QT interval corrected by Fridericia's formula) must be used for each individual participant to determine eligibility for and discontinuation from the study. This formula may not be changed or substituted once the participant has been enrolled.
- The QTcF must be continued to be used for all QTc data being collected from all subjects for data analysis. Safety ECGs and other non-protocol specified ECGs are an exception.
- The QTc should be based on single or averaged QTc values of triplicate electrocardiograms obtained over a brief (e.g., 5-10 minutes) recording period.
- For this study, the following QTc stopping criteria will apply:
  - QTcF  $> 500$  msec or uncorrected QT  $> 600$  msec
  - For patients with bundle branch block: QTcF  $\geq 530$  msec

- Change from baseline in QTcF > 60 msec

See the SoA for data to be collected at the time of treatment discontinuation and follow-up and for any further evaluations that need to be completed.

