5.2. Baseline Definitions

For all endpoints (except as noted in baseline definitions) the baseline value will be the latest pre-dose assessment with a non-missing value, including those from unscheduled visits. If time is not collected, Day 1 assessments (except any assessments from unscheduled visit at the same date as Day1) are assumed to be taken prior to first dose and used as baseline.

Unless otherwise stated, if baseline data is missing no derivation will be performed and baseline will be set to missing.

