11.5.2. Reporting Standards

General

 The current GSK Integrated Data Standards Library (IDSL) will be applied for reporting, unless otherwise stated (IDSL Standards Location: https://spope.gsk.com/sites/IDSLLibrary/SitePages/Home.aspx): 
 4.03 to 4.23: General Principles 5.01 to 5.08: Principles Related to Data Listings 6.01 to 6.11: Principles Related to Summary Tables 7.01 to 7.13: Principles Related to Graphics
Formats

 GSK IDSL Statistical Principles (5.03 & 6.06.3) for decimal places (DP's) will be adopted for reporting of data based on the raw data collected, unless otherwise stated. Numeric data will be reported at the precision collected on the eCRF. The reported precision from non eCRF sources will follow the IDSL statistical principles but may be adjusted to a clinically interpretable number of DP's.
Planned and Actual Time

 Reporting for tables, figures and formal statistical analyses: 
 Planned time relative to dosing will be used in figures, summaries, statistical analyses and calculation of any derived parameters, unless otherwise stated. The impact of any major deviation from the planned assessment times and/or scheduled visit days on the analyses and interpretation of the results will be assessed as appropriate. Reporting for Data Listings: 
 Planned and actual time relative to study drug dosing will be shown in listings (Refer to IDSL Statistical Principle 5.05.1). Unscheduled or unplanned readings will be presented within the subject's listings.
Unscheduled Visits

 Unscheduled visits will not be included in summary tables and/or figures except as part of a 'worst case post-baseline' assessment.

• All unscheduled visits will be included in listings.	
Descriptive Summary Statistics	
Continuous Data	Refer to IDSL Statistical Principle 6.06.1
Categorical Data	N, n, frequency, %
Graphical Displays	
• Refer to IDSL Statistical Principals 7.01 to 7.13.	

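### SAP 8.6.2 counts ECGs with a technical error as valid, so artefacts can appear as QTcF signals and a faulty baseline can hide a real rise

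*SAP*

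**What the plan says.** SAP 8.6.2 makes no quality distinction between tracings: "All ECG data present in the database will be considered valid and will be reported (even if the ECG had a technical error". On timing it says "12-lead ECGs are measured at Visit 1, 3, 5 and 7, and at Early Withdrawal visit", which gives one scheduled pre-dose ECG and three scheduled on-treatment ECGs for a participant who completes.

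The maximum post-baseline QTcF, PR interval and heart rate each "will be derived as the maximum on-treatment value recorded at any scheduled, unscheduled, or EW visit after the start of study treatment". QTcF values, including that maximum, are then put into categories with cut-points at 450, 480, 500 and 530 msec. Changes from baseline, including the change to the maximum, are put into categories ending at more than 60 msec.

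For baseline, SAP 5.2 says "the baseline value will be the latest pre-dose assessment with a non-missing value, including those from unscheduled visits", again without a quality condition. SAP 11.5.2 adds: "Unscheduled visits will not be included in summary tables and/or figures except as part of a 'worst case post-baseline' assessment".

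Protocol 8.1.2 lists "Change from baseline in QTcF > 60 msec" and a QTcF above 500 msec among its stopping criteria, so two of the SAP's cut-points coincide with them. The 12-lead ECG is a secondary safety endpoint (Protocol section 4).

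**The concern.** A maximum over several tracings is the summary most exposed to a single wrong value, and this rule keeps values known to be technically wrong. A faulty tracing with a long QTcF can become the participant's maximum and put that participant in the top category.

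The rule is not simply cautious, because it also covers baseline. One faulty baseline shifts every change value for that participant. If it is falsely short, it creates rises; if it is falsely long, it hides them.

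The setting makes a few wrong entries matter more. There is no control arm against which to judge a background artefact rate. The final tables divide about 110 participants into three dose groups with no target allocation ratio (SAP 2.3 and 5.1.2.1), so one entry can weigh heavily in a small column. The interim tables are intended for the JNDA submission (Protocol 10.3.4). What is at stake is whether a reader can tell a QTcF finding from a recording fault.

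**Working it through.** The plan states no figure that depends on this rule, so there is none to reproduce. The check has two parts: following the rule through the text, then showing its possible scale under stated assumptions.

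**Following the rule.**

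- Observed change = true change + on-treatment error - baseline error. SAP 8.6.2 admits the first error and SAP 5.2 does not screen out the second.
- No SAP section excludes or flags technical-error tracings, or plans a table without them.
- SAP 8.6.2 treats the ECG interpretation differently. A participant is classed as unable to be evaluated only if every on-treatment tracing is so rated, so one evaluable tracing overrides the others. For the numeric maximum, a valid tracing does not override a faulty one.
- The general rule for several values at one time point (SAP 11.6.1: nearest the target day, mean if tied) selects by timing, not by quality.

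**Inputs.**

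- N = 110 enrolled (Protocol 10.1).
- Three scheduled on-treatment ECGs, at Visits 3, 5 and 7, and one pre-dose ECG at Visit 1 (Protocol Table 1; SAP 8.6.2).
- q = share of tracings with a technical error. Assumption.
- f = share of faulty tracings that falsely give a change above 60 msec. Assumption.
- Errors are taken as independent, and all 110 participants as having all three on-treatment ECGs.

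**Step 1: participants with at least one faulty on-treatment tracing eligible to be the maximum.** Formula: 110 x [1 - (1 - q)^3].

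- q = 1%: 1 - 0.99^3 = 0.0297; x 110 = 3.3.
- q = 3%: 1 - 0.97^3 = 0.0873; x 110 = 9.6.

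At the Week 24 interim only Visits 3 and 5 contribute, so the exponent is 2: 110 x 0.0199 = 2.2 and 110 x 0.0591 = 6.5.

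**Step 2: participants falsely above 60 msec.** Formula: p = 1 - (1 - qf)^3; expected number 110p; chance of at least one 1 - (1 - p)^110.

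| q | f | Expected, maximum row | Expected, one visit row (110qf) | Chance of at least one in the maximum row |
|---|---|---|---|---|
| 0.5% | 10% | 0.16 | 0.06 | 15% |
| 1% | 25% | 0.82 | 0.28 | 56% |
| 2% | 50% | 3.27 | 1.10 | 96% |

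The maximum row gathers about three times as many false cases as any single visit row. Steps 1 and 2 use different ranges of q and answer different questions. Step 1 counts exposure to the problem; step 2 counts its effect.

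**Step 3: baseline.** With one scheduled pre-dose ECG, 110q = 1.1 to 3.3 participants would have a faulty Visit 1 tracing at q = 1-3%. This is an upper figure, because a repeat before dosing becomes the baseline under SAP 5.2.

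**The case against.** The case for leaving the rule alone has real weight.

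- **It is explicit and pre-specified.** In an open-label study, removing values by flag opens the way to dropping a real prolongation. The documents define no criteria for a technical error and name nobody to assign it. For the maximum, keeping everything errs towards over-reporting. This stands, and it is why the all-tracings tables should remain.
- **A faulty baseline may be replaced.** SAP 5.2 takes the latest pre-dose value, unscheduled visits included, and the investigator reviews the screening ECG for eligibility (Protocol 6.2, criterion 8). This stands too: the baseline problem is confined to faulty tracings not repeated before dosing.
- **Conduct has its own check.** Protocol 9.4.3 asks for triplicates once a stopping criterion is met, and Protocol 8.1.2 allows averaged values. That protects decisions about participants. It does not correct the table, because SAP 8.6.2 takes the largest recorded value and does not say that an average replaces the first one.
- **Nothing inferential depends on it.** There are no hypotheses, and by-visit values are tabulated separately. This limits the importance of the point. The sponsor's core data standards, which SAP 8.6 invokes, might say more but are not in the documents.

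A reader might go further and infer that artefacts will appear as signals, will dominate the top categories, or will distort stopping decisions. The documents support none of these. They give no error rate, do not say whether a faulty tracing carries a numeric QTcF, and do not indicate the direction of error. No SAP table feeds a stopping decision.

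**Conclusion.** The point holds as a modest one. The SAP states a rule under which a tracing known to be faulty can set the baseline, a by-visit value, the maximum QTcF and its category, and it provides no display that shows the effect. Artefacts can therefore appear as QTcF signals, and an unrepeated, falsely long baseline can hide a real rise.

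The size cannot be determined from the documents. The 3-10 of 110 with an eligible faulty tracing assumes a 1-3% error rate and must not be read as false signals. The 0.2-3.3 false cases above 60 msec assume 0.5-2% faulty tracings, of which 10-50% falsely cross the threshold. No equivalent was calculated for the entries above 500 msec. The consequence is confined to descriptive tables of a secondary safety endpoint, so this is a worthwhile low-cost improvement and not a fault that undermines the study.

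**What to change.** 1. Keep the planned all-tracings tables unchanged (2.28-2.31 at interim, 12.47-12.50 at final).
2. Add to SAP 8.6.2 a parallel version of the QTcF value and change-category tables, including the maximum. It should omit tracings recorded as technical errors from the baseline and post-baseline derivations where a valid tracing exists.
3. State that technical-error status is assigned from tracing quality only, without regard to the QTcF value.
4. Show that status in listings 28/29 and 72/73. These listings are built around participants with abnormal findings, so a footnote to each parallel table should also give the number of tracings omitted.
5. Footnote the number of participants with no valid tracing to substitute. This matters most at baseline: with one scheduled pre-dose ECG, an unrepeated faulty baseline can be disclosed but not corrected.

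The cost is a short SAP addition, one filter and a few extra descriptive tables. Some cells will hold slightly fewer values. There is also a risk of omitting a real prolongation from the parallel version, which the retained all-tracings tables cover.
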